### 3.3 Handling of outliers

The final efficacy analysis will be preceded by a blind data review (BDR) which consists of individual graphs per visit by time of all efficacy measurements. The graphs will be used to detect outliers and measurements unsuitable for analysis. All data points to be removed or changed before analysis will be noted and justified on the form "Excluded subjects and data" and this will be signed by the statistician and the principal investigator before database lock.

### 3.4 Handling of protocol deviations

Subjects with protocol deviations will not be excluded from the analyses of the safety data (except in the case of subjects with all post-baseline safety data missing); such subjects may be excluded from the analysis of the efficacy data at the discretion of the responsible statistician and principal investigator, blinded to treatment allocation (subjects not excluded are then referred to as the Per-Protocol population, see 4.1.3). This will also be noted on the form "Excluded subjects and data".

### 3.5 Assignment of preferred terms to original terminology

The original terms used by the investigator will be assigned preferred terms for classification and tabulation. The following dictionary databases will be used for assigning preferred terms:

- AEs/SAEs: MedDRA Version 21.1 or higher
- Previous/Concomitant Medications: WHO-ATC/WHO Drug B3 format of March 2019

### 3.6 Reporting conventions

P-values  $\geq 0.0001$  will be reported to 4 decimal places; P-values less than 0.0001 will be reported as "<0.0001". Upper case is used for P-value. The mean, standard deviation (SD), and any other statistics other than quantiles, will be reported to one decimal place greater than the original data. Quantiles, such as median, or minimum (Min) and maximum (Max) will use the same number of decimal places as the original data. Estimated parameters, not on the same scale as raw observations (e.g. regression coefficients) will be reported to 3 significant figures. Confidence limits (abbreviated CLs) will be separated by a hyphen, e.g., xxx - xxx).

Tables and listings are programmed following the following rules:

Final deliverable	Word 2010 document (docx)			
Page Option	Landscape		Portrait	
Courier New Font	Number of cols	Number of lines	Number of cols	Number of lines
8	150	45	100	70

Graphic outputs will be produced in png or emf format.

Subjects randomized to Placebo group at each cohort will be pooled and represented only one study group in any reporting outputs.

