## 4.2 Subject disposition

The following subject data will be listed by subject and summarized by study part:

- Screened participants: all participants who have signed the informed consent
- Randomized participants: participants who receive a randomization number
- The safety population
- The mITT population
- The PP population

For the following two categories of participants, counts, and percentages will be calculated for each treatment group using the number of randomized participants in each group as denominator.

- Participants who have completed the treatment period
- Participants who discontinued the study drug during the treatment period

A list of participants prematurely withdrawn from the study, along with reasons for discontinuation, will be provided. Reason for withdrawal will be tabulated using count and percentage of participants by treatment group and overall. A participant must be withdrawn from the study for any of the following reasons:

 
▪ Adverse event
 
▪ Screen failure
 
	
 
▪ Study terminated by sponsor
 
▪ Pregnancy
 

---	--

- Withdrawal by subject
- Lost to follow-up
- Physician decision
- Protocol deviation
- Death
- Other
- Reserve subject

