### 4.3 Baseline characteristics

#### 4.3.1 Demographics and baseline variables

Demographic and baseline disease characteristics data (only applicable for part B, being Hoehn & Yahr stage and disease duration) will be summarized by treatment group and overall for the safety population in each study part.

Continuous demographic and baseline disease characteristics (e.g., age, height, weight, BMI) will be summarized by using descriptive statistics (n, mean, SD, median, Min, Max).

Qualitative demographic characteristics (gender, race) will be summarized by counts and percentages.

Demographics data will also be listed. The listing will include subject number, date of informed consent, date of dosing, treatment, age of subject, gender, race, height, weight and BMI.

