#### 4.4.1 Adverse events

The AE coding dictionary for this study will be Medical Dictionary for Regulatory Activities (MedDRA). It will be used to summarize AEs by primary system organ class (SOC) and preferred term (PT).

The observation period will be divided into 2 segments: pre-treatment and post-treatment.

- The pre-treatment period is defined as the time from the date of the informed consent to the time before the administration of first dose of study medication.

- The post-treatment period is defined as the time from after the first dose of study medication to the end of the study.

Pre-treatment AEs are defined as AEs that develop or worsen or become serious during the pre-treatment period.

Treatment-emergent AEs (TEAEs) are defined as AEs that develop or worsen (according to the investigator's judgement) or become serious during the post-treatment period.

The primary focus of adverse event reporting in the CSR will be TEAEs. Pre-treatment AEs will be described separately.

All AEs and SAEs will be displayed in listings. The listing will contain subject number, treatment, occasion, dosing date, SOC, PT, start date and time of AE, duration of AE, severity, SAE, relationship and chronicity.

Summaries of all TEAEs in each treatment group and overall (pooled Placebo versus pooled treatment groups), will include:

- The overview of AEs, summarizing number (%) of subjects with any TEAE/serious TEAE.
- The number and percentage of subjects with at least one TEAE by System-organ Class and Preferred Term.
- Summary of TEAEs by intensity (mild, moderate, severe, life-threatening, death), presented by System-organ Class and Preferred Term.
- Summary of TEAEs by causal relationship to the study drug, by System-organ Class and Preferred Term.

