#### 4.5 Analysis of efficacy endpoints

All observed and change from baseline efficacy endpoints will be listed by treatment group, subject and visit. Individual graphs by visit will also be generated.

All observed and change from baseline efficacy endpoints with multiple post-baseline measurements (including but not limited to levels of anti-aSyn, anti-UBITH and anti-CpG1 antibody titers in serum and their antibody parameters of  $C_{max}$ ,  $t_{max}$ ,  $AUC_{last}$  and  $t_{1/2}$ , which are derived by non-compartmental analysis and total and free aSyn concentrations in blood) will be summarized using descriptive statistics of n, mean, SD, SEM, median, Min and Max by treatment group, visit (and time when applicable), and will also be presented graphically as mean over time, with standard deviation as error bars.

All observed and change from baseline efficacy endpoints with single post-baseline measurement (including but not limited to levels of anti-aSyn, anti-UBITH and anti-CpG1 antibody titers in CSF and their antibody parameters of  $C_{max}$ ,  $t_{max}$ ,  $AUC_{last}$  and  $t_{1/2}$ , which are derived by non-compartmental analysis and total and free aSyn concentrations in CSF, T-cell ELISpot specific for the immunizing peptide as well as MDS-UPDRS Parts II and III sub scores and total scores) will be summarized using descriptive statistics of n, mean, SD, SEM, median, Min and Max by treatment group, and will also be presented graphically as mean in a bar graph, with standard deviation as error bars.

To establish whether significant treatment effects can be detected on the observed efficacy endpoints with multiple post-baseline measurements, such as serum levels of anti-aSyn, anti-UBITH and anti-CpG1 antibody titers in blood, each parameter will be analysed with a mixed model analysis of covariance (ANCOVA) with treatment, time and treatment by time as fixed factors and subject as random factor and the (average) baseline measurement as covariate.

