The efficacy endpoints of levels of anti-aSyn, anti-UBITH and anti-CpG1 antibody titers in serum and in CSF will initially be analysed without transformation, but if the data suggest otherwise, log-transformation may be applied. Log-transformed parameters will be back-transformed after analysis where the results may be interpreted as percentage change. Residual Q-Q plots are produced to check the assumption of normality of the error term in the mixed effects models as described above. This is done by visual inspection and the Shapiro-Wilk test statistic.

The observed efficacy endpoints with single post-baseline measurement, such as levels of anti-aSyn, anti-UBITH and anti-CpG1 antibody titers in CSF, will be analysed with a mixed model analysis of variance (ANOVA) with treatment as fixed factors and subject as random factor and the (average) baseline measurement as covariate.

The Kenward-Roger approximation will be used to estimate denominator degrees of freedom and model parameters will be estimated using the restricted maximum likelihood method.

The general treatment effect and specific contrasts will be reported with the estimated difference and the 95% confidence interval, the least square mean estimates and the p-value. Graphs of the Least Squares Means (LSM) estimates over time by treatment group will be presented with 95% confidence intervals as error bars, as well as change from baseline LSM estimates.

The following contrasts will be calculated within the model using observed data:

- Treatment with 3 vaccinations of 40 $\mu$ g UB-312 versus pooled Placebo
- Treatment with 3 vaccinations of 100  $\mu$ g UB-312 versus pooled Placebo
- Treatment with 1 vaccination of 40  $\mu$ g, followed by 2 vaccinations of 300  $\mu$ g UB-312 versus pooled Placebo
- Treatment with 3 vaccinations of 300  $\mu$ g UB-312 versus pooled Placebo
- Treatment with 1 vaccination of 40  $\mu$ g, followed by 2 vaccinations of 1000  $\mu$ g UB-312 versus pooled Placebo
- Treatment with 3 vaccinations of 1000  $\mu$ g UB-312 versus pooled Placebo
- Treatment with 3 vaccinations of 2000  $\mu$ g UB-312 versus pooled Placebo

Notes:

- (1) Change from baseline values calculated at subject level for each efficacy endpoint will only be used for descriptive purposes.
- (2) Above contrast will be adjusted to obtain for change from baseline endpoints.
- (3) The treatment groups across the cohorts will also be compared pairwise.

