## APPENDIX 2 PROCEDURE & SYNTAX

Analysis	Procedure and Code
AN(C)OVA	
For the SAS script:
 
 
▪ period = occasion
 
▪ time = expdelta
 
▪ subject = subjectnr
 
▪ baseline=pre&var
 
 
SAS Proc MIXED Procedure:
 
Repeatedly measured:
 <pre>proc mixed data=mix order=internal nobound ; class subjectnr treatment expdelta occasion ; model &var=treatment occasion expdelta treatment*expdelta pre&var/ ddfm=KR; random subjectnr subjectnr*treatment subjectnr*expdelta/type=vc ; run;</pre> 
Single measured:
 <pre>proc mixed data=mix order=internal nobound ; class subjectnr treatment occasion ; model &var=treatment occasion pre&var/ ddfm=KR; random subjectnr/type=vc ; run;</pre>

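### SAP v2.0 pools placebo across all cohorts without regard to study part and names no Part B contrasts, so read literally every arm is compared with 8 healthy plus 6 PD participants

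*SAP*

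**What the plan says.** The SAP's document history gives the reason for version 2.0 as bringing it into line with the latest protocol for Part B. On pooling and comparators it says the following.

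- **Section 3.6, placebo:** "Subjects randomized to Placebo group at each cohort will be pooled and represented only one study group in any reporting outputs". Study part is not mentioned.
- **Section 4.4.1, adverse events:** "Summaries of all TEAEs in each treatment group and overall (pooled Placebo versus pooled treatment groups), will include". Study part is again not mentioned.
- **Section 4.5, model:** a mixed ANCOVA "with treatment, time and treatment by time as fixed factors and subject as random factor", with baseline as covariate. The Appendix 2 code for repeated measures has the class variables "class subjectnr treatment expdelta occasion". Neither has a term for study part or population.
- **Section 4.5, contrasts:** the list introduced by "The following contrasts will be calculated within the model using observed data" has seven entries, each a UB-312 regimen against pooled placebo. They match Cohorts 1 to 7 in section 1.10. Note (3) adds: "The treatment groups across the cohorts will also be compared pairwise".

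Other sections do separate the parts. Disposition (4.2): "The following subject data will be listed by subject and summarized by study part". Demographics and baseline (4.3.1): "will be summarized by treatment group and overall for the safety population in each study part". Treatment tolerability (4.3.4) is also defined for each part. Section 1.11.3 plans an end-of-treatment analysis for Part B but names no comparator.

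**The concern.** Healthy placebo participants are not a randomised control for the PD arms. They come from a different population with different entry criteria. Under the protocol's study design, Part B starts only after every Part A participant has completed the Week 21 assessments, so the treatment periods do not overlap either. If section 3.6 is followed, each arm is compared with a placebo group whose population mix differs from its own. Any background difference between healthy and PD participants then appears as a treatment difference, with opposite signs in Part A and Part B arms.

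The Part B comparisons are also unspecified. The Cohort 8 regimen (300/100/100 µg) has no contrast. Three vaccinations of 300 µg describes both Cohort 4 (6 healthy active) and Cohort 9 (7 PD active), and the SAP does not say which is meant or whether they form one treatment level. A programmer following 3.6 would build one placebo column of 14; one following 4.3.1 would build two.

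The exposure is greatest for adverse events, which serve the first primary objective, and for laboratory values and aSyn levels. It is probably smaller for antibody titers, where the baseline covariate and possibly low placebo titers limit it. MDS-UPDRS and MoCA are collected only in Part B, so healthy placebo data cannot enter those comparisons.

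**Working it through.** **Counts** (protocol synopsis; table in SAP 1.10)

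| | Active | Placebo |
|---|---|---|
| Part A, healthy | 7 × 6 = 42 | 2 + 6 × 1 = 8 |
| Part B, PD | 2 × 7 = 14 | 2 × 3 = 6 |

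Totals are 42 + 8 = 50 healthy and 14 + 6 = 20 PD, which reproduce the planned 50 and 20 in SAP 1.9.

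**Shift with no drug effect.** Let d be the PD-minus-healthy difference in background incidence. The expected difference between two groups is d times the difference in their PD shares. The PD share is 14/56 = 0.250 in pooled active, 6/14 = 0.429 in pooled placebo, and 7/13 = 0.538 if Cohorts 4 and 9 are merged. The documents give no value for d; the last column assumes 10 to 50 percentage points.

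| Comparison with all 14 placebo | Shift | Points |
|---|---|---|
| Pooled active | 0.250 - 0.429 = -0.179d | -1.8 to -8.9 |
| One PD cohort | 1 - 0.429 = +0.571d | +5.7 to +28.6 |
| One Part A cohort | 0 - 0.429 = -0.429d | -4.3 to -21.4 |
| Cohorts 4 + 9, if merged | 0.538 - 0.429 = +0.110d | +1.1 to +5.5 |

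**Effect of the baseline covariate.** Assume a stable healthy-PD difference of 1 within-population SD, one post-baseline value, and baseline/post correlation r. With ten groups (nine active cohorts and one placebo pool of 14), the within-group baseline sum of squares is about 70 - 10 = 60. The population split inside the placebo pool adds 8 × 6/14 = 3.43. The fitted slope is about (60r + 3.43)/63.43, and the PD-arm shift is 0.571 × (1 - slope).

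| r | Slope | PD-arm shift, SD |
|---|---|---|
| unadjusted | - | 0.57 |
| 0.5 | 0.527 | 0.27 |
| 0.7 | 0.716 | 0.16 |
| 0.9 | 0.905 | 0.05 |

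Simulated ANCOVAs of the same set-up agree: 0.27, 0.16 and 0.05 to 0.06 SD.

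**Precision.** SE in SD units is √(1/n active + 1/n placebo).

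- Part B arm: √(1/7 + 1/14) = 0.463 against all placebo; √(1/7 + 1/6) = 0.556 within part; ratio 1.20.
- Part A arm: √(1/6 + 1/14) = 0.488 against all placebo; √(1/6 + 1/8) = 0.540 within part; ratio 1.11.

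Fitting Part B separately also lowers the residual degrees of freedom, with a single post-baseline value, from 70 - 11 = 59 to 20 - 4 = 16. The 95% t quantile rises from 2.001 to 2.120, so the interval widens by 1.20 × 2.120/2.001 = 1.27.

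**The case against.** The strongest reply is that pooling within part was intended. The sentence in 3.6 closes a section on decimals, fonts and file types and never says that placebo is pooled across parts. Three other sections report by part, and the Part A interim and the Part B end-of-treatment analysis are planned separately. The contrast list looks like Part A text that was not updated. The code looks generic (it carries an occasion term in a parallel-group study), and run separately by part it would need no part term. Nothing states that Cohorts 4 and 9 are merged. Some protocol and SAP text was not available for this review, so a by-part rule elsewhere cannot be excluded.

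Much of this is fair, and incomplete updating is the likely cause. It does not cure the defect: 3.6 applies to any reporting output, and the adverse event and model sections do not limit it. A by-part rule elsewhere would still have to be reconciled with it. The merged-cohort figure shows only what one reading would do.

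A second reply concerns size. The range for d is assumed. For 7 against 14 participants at 50% incidence the SE is √(0.25/7 + 0.25/14) = 0.23, or 23 points, so much of the range lies within sampling error. For continuous endpoints, approximate mean squared error (squared shift plus (1 - r²) × SE²) does not favour splitting under the 1 SD assumption:

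- r = 0.5: pooled 0.270² + 0.75 × 0.463² = 0.234; within part 0.75 × 0.556² = 0.232.
- r = 0.7: pooled 0.162² + 0.51 × 0.463² = 0.136; within part 0.51 × 0.556² = 0.158.

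That stands as a limit on the concern for baseline-adjusted endpoints. It does not extend to adverse event tables, which have no adjustment, or to the unnamed Part B contrasts.

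Finally, section 4.5.1 sets no formal hypothesis, and adverse events are also listed by subject, so a by-part table could be made later. That lowers the stakes, but 95% intervals and p-values will still be reported.

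**Conclusion.** The concern holds and should be fixed. As written, the SAP pools 8 healthy and 6 PD placebo participants into one comparator, conflicts with its own by-part sections, and leaves the Part B placebo comparisons unnamed (unspecified, not absent). The signs and weights of the shifts (-0.179d, +0.571d, -0.429d) follow from the allocation alone. Their size depends on d, which the documents do not give. For continuous endpoints, under an assumed stable 1 SD difference and correlations of 0.5 to 0.9, the PD-arm shift falls from 0.57 SD to between 0.27 and 0.05 SD. Confidence is medium, because pooling within part was probably intended and some text was not available. The effect is on the reading of estimates and safety tables, not on a confirmatory error rate.

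**What to change.** - **3.6:** state that placebo is pooled within study part only (n = 8 in Part A, n = 6 in Part B).
- **4.5 and Appendix 2:** state that the parts are analysed separately, with Cohorts 4 and 9 as distinct treatment levels. Add two contrasts: Cohort 8 versus Part B placebo and Cohort 9 versus Part B placebo. Say whether note (3) applies within part.
- **4.4:** present adverse event and other safety summaries by study part, as 4.2, 4.3.1 and 4.3.4 already do.
- **1.10 (clerical, carries no weight in this point):** the text assigns twelve PD participants to Cohort 8, while the table below it and the protocol synopsis give 7 + 3 in each of Cohorts 8 and 9. These must be reconciled.

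The drafting cost is a few sentences and two contrast statements. The statistical cost is precision: SE rises about 20% for a Part B arm and 11% for a Part A arm, and the Part B interval widens by about 27% when that part is fitted alone. Fitting both parts in one model with a part term would avoid some of the loss of degrees of freedom. If that is preferred, the SAP should say so and still define the Part B contrasts against Part B placebo.

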## 4 STATISTICAL METHODOLOGY AND ANALYSES

### 4.1 Analysis Sets

The analyses of immunogenicity and efficacy endpoints will be performed by the treatment allocation and based on the modified Intention-to-Treat (mITT) and Per-Protocol (PP) populations as defined below. If both populations are identical, results will only be presented for mITT population.

Safety endpoints and tolerability will be analysed based on the safety population as defined below.

#### 4.1.1 Safety population

The safety population is the total treated population defined as all participants randomized and exposed to at least one dose of the study drug, regardless of the amount of treatment administered.

#### 4.1.2 Modified Intention-to-Treat (mITT) population

Modified intention-to-treat (mITT) population consists of all randomized participants who receive at least one dose of the study drug and have both baseline and at least one post-baseline assessment in any of the primary or secondary variables, irrespective of compliance with the study protocol and procedures.

#### 4.1.3 Per-Protocol (PP) population

Per-protocol (PP) population includes all participants who receive all planned doses of the study drug, complete the treatment period, fulfil all entry criteria, and have no critical or major protocol deviations (as described in Table 1 of Protocol Deviation Handling Plan) that requires exclusion of the participant. Prior to database lock, all protocol deviations will be determined and reviewed, and CHDR and UNS will jointly decide whether the deviations require a participant to be excluded from the efficacy analysis population.

## 4.2 Subject disposition

The following subject data will be listed by subject and summarized by study part:

- Screened participants: all participants who have signed the informed consent
- Randomized participants: participants who receive a randomization number
- The safety population
- The mITT population
- The PP population

For the following two categories of participants, counts, and percentages will be calculated for each treatment group using the number of randomized participants in each group as denominator.

- Participants who have completed the treatment period
- Participants who discontinued the study drug during the treatment period

A list of participants prematurely withdrawn from the study, along with reasons for discontinuation, will be provided. Reason for withdrawal will be tabulated using count and percentage of participants by treatment group and overall. A participant must be withdrawn from the study for any of the following reasons:

 
▪ Adverse event
 
▪ Screen failure
 
	
 
▪ Study terminated by sponsor
 
▪ Pregnancy
 

---	--

- Withdrawal by subject
- Lost to follow-up
- Physician decision
- Protocol deviation
- Death
- Other
- Reserve subject

### 4.3 Baseline characteristics

#### 4.3.1 Demographics and baseline variables

Demographic and baseline disease characteristics data (only applicable for part B, being Hoehn & Yahr stage and disease duration) will be summarized by treatment group and overall for the safety population in each study part.

Continuous demographic and baseline disease characteristics (e.g., age, height, weight, BMI) will be summarized by using descriptive statistics (n, mean, SD, median, Min, Max).

Qualitative demographic characteristics (gender, race) will be summarized by counts and percentages.

Demographics data will also be listed. The listing will include subject number, date of informed consent, date of dosing, treatment, age of subject, gender, race, height, weight and BMI.

